4.1 Inclusion criteria

4.1.1 At individual patient level

- Post-approval: Patients over 80 years old presenting with acute ischaemic stroke symptoms for which thrombolysis treatment with alteplase (Actilyse®) from 1 July 2018 or the first day of the next month after exact approval date, if later, and treatment was initiated within 4.5 hours after stroke onset according to SmPC are included. (see appendix 2)
- Pre-approval: Patients over 80 years who received thrombolysis with alteplase (Actilyse®) otherwise according to SmPC for AIS within 4.5 hours after stroke onset during the period (approximately 3 years) prior to July 2018 or the exact approval date, if later, are included.

4.1.2 At centre level

- A typical experience from acute stroke treatment defined by at least 5 patients treated with IVT and entered in the SITS-ISTR in both pre and post approval groups
- At least 70% data entered at 3m follow up) in both pre and post approval groups
- A willingness to participate in SITS-IVT>80 years registry

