## **8. RESEARCH QUESTION AND OBJECTIVES**

Safety and efficacy of a treatment in acute ischaemic stroke may be different in the RCT settings in patients over 80 years. Although IVT in patients >80 years has been used off-label in many countries prior to approval, use of IVT in patients >80 years will probably be more frequent after approval. The SITS-ISTR provides an opportunity for continuous monitoring of thrombolysis treatment in stroke, and provides a technical foundation for the SITS->80 years post-approval registry. The proposed SITS-IVT>80 years is a retrospective study of existing data in the SITS-ISTR for the ischaemic stroke patients treated with IVT according to the Summary of Product Characteristics (SmPC) criteria. The study aims to evaluate the incidence rate of SICH, death and independence/favourable outcome within 90 days for ischaemic stroke patients treated with rt-PA in clinical routine settings. At least 2000 (1000 in the post-approval and 1000 in the pre-approval) patients overall from approximately 60 European sites are planned to be identified in the SITS-IVT>80 years study. Safety and other outcome parameters will be compared between post-approval >80 years and pre-approval >80 years patients.

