## 9.8        **QUALITY CONTROL**

European Stroke Centres (approx. 60) continuously registering patients into SITS-ISTR having

- a typical experience from acute stroke treatment
- high quality (at least 90% complete data entered at acute phase and 70% data entered at 3m follow up) in both prospective and retrospective groups
- a willingness to participate in SITS-IVT>80 years registry

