2 RESEARCH QUESTIONS AND OBJECTIVES

2.1 Primary objective:

The SITS (Safe Implementation of Treatment in Stroke) Intravenous thrombolysis (IVT) with alteplase >80 years study will primarily investigate the safety and outcome of IVT in acute ischaemic stroke in patients >80 years collected during the post- approval period and to compare the safety and outcome with

existing pre-approval patients >80 years collected in routine clinical practice and recorded in the SITS-ISTR (International Stroke Thrombolysis Registry).

2.2 Secondary objectives:

We will describe patient's characteristics, management time: onset of symptoms to time of treatment initiation, and its components: onset of symptoms to door; door to treatment initiation.

3 Definitions and Outcome Measurements/Variables

3.1 Definitions:

- **Index event** is defined as the date/time of initiation of stroke onset
- **Treatment:** IV thrombolysis with alteplase (Actilyse®).
- **Baseline visit:** day of hospital admission for ischaemic stroke
- The **3 month follow-up data point** for patients is 90 (+/- 10) days after the index event.
- **Post-approval:** Patients >80 years old presenting with acute ischaemic stroke symptoms for which thrombolysis treatment was initiated within 4.5 hours after stroke onset according to the SmPC during the study period July 2018 to June 2021.
- **Pre-approval:** Patients >80 years presenting with acute ischaemic stroke symptoms for which thrombolysis treatment was initiated within 4.5 hours after stroke onset otherwise according to SmPC during the period of approximately 3 years prior to approval (June 2015 to June 2018)

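### The centre rule of at least 5 patients in both periods limits the post-approval incidence estimates to centres with registered over-80 use before approval

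*SAP*

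**What the plan says.** The primary objective in SAP 2.1 has two parts. The study "will primarily investigate the safety and outcome of IVT in acute ischaemic stroke in patients >80 years collected during the post- approval period", and it then compares these patients with the pre-approval patients.

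SAP 3.1 defines the two groups by age as well as by period. The post-approval definition opens with "Patients >80 years old presenting with acute ischaemic stroke symptoms for which thrombolysis treatment was initiated within 4.5 hours after stroke onset according to the" and goes on to name the label and the dates. The pre-approval group is "Patients >80 years presenting with acute ischaemic stroke symptoms for which thrombolysis treatment was initiated within 4.5 hours after stroke onset otherwise according to SmPC".

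SAP 4.1.2 sets the centre criteria within the inclusion criteria. Typical experience is defined as "at least 5 patients treated with IVT and entered in the SITS-ISTR in both pre and post approval groups". The next criterion is "At least 70% data entered at 3m follow up) in both pre and post approval groups". The third is willingness to take part.

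Protocol 9.8 asks for "a typical experience from acute stroke treatment" and gives no count. It also asks for at least 90% complete acute-phase data and 70% of three-month data in both the prospective and the retrospective group.

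Protocol 9.7.1 promises incidence with a 95% CI in each cohort, on the matched and the unmatched sets. The SAP (Planned Analysis) reports outcomes separately by period, with Wilson intervals for binary outcomes.

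**The concern.** Protocol 8 motivates the study by noting that over-80s were treated off-label before approval and that "use of IVT in patients >80 years will probably be more frequent after approval". A post-approval study should therefore be able to describe outcomes wherever registered over-80 patients were treated after approval. The SAP rule makes a centre's post-approval patients depend on its pre-approval record. A centre that began treating or registering over-80s only after approval cannot contribute, however many patients it has.

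What is at stake is whom the post-approval incidence describes. The SAP's section on limitations discusses selection bias at patient level only. The planned sensitivity analyses vary the propensity covariates or restrict by region, and none relaxes the centre rule. The SAP also names growing experience as a possible explanation for a period difference, so it treats experience as relevant while leaving out centres with little or no registered pre-approval experience in this age group.

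**Working it through.** There is no planned figure to reproduce. The threshold of 5 has no stated derivation, and the sample size is not based on a power calculation.

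**Step 1: who is excluded.** Apply the criteria to a centre with adequate post-approval data, by its number of registered over-80 patients before approval.

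| Pre-approval over-80s | Protocol 9.8 completeness in both groups | SAP count of 5 |
|---|---|---|
| 0 | cannot be shown (no denominator) | fails |
| 1-4 | can be met (for example 3 of 4 = 75% at three months) | fails |
| 5 or more | can be met | passes |

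The 0 row is already a difficulty under the protocol. The 1-4 row is what the SAP's count adds.

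**Step 2: which estimates are affected.** Because the rule is an inclusion criterion, it applies to the matched set, the unmatched set and the descriptive incidence in each cohort. No planned estimate covers the excluded centres.

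**Step 3: how often a centre might fall below 5.** The inputs are about 60 centres (protocol 9.8) and about 1000 patients per period, with a minimum of 500 (SAP 4). The means are 1000/60 = 16.7 and 500/60 = 8.3 per centre per period. Applying 60 centres to both totals is a simplification, since the 1000 may include patients from outside the mutual-recognition countries. The spread of centre sizes is not given, so it is assumed.

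| Assumed spread | P(fewer than 5), mean 16.7 | P(fewer than 5), mean 8.3 |
|---|---|---|
| Poisson (equal-sized centres) | 0.02% | 8% |
| Negative binomial, dispersion 2 | 13% | 33% |
| Negative binomial, dispersion 1 | 25% | 43% |

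For dispersion 1, P = 1 - (m/(1+m))^5. With m = 16.7 this is 1 - (16.7/17.7)^5 = 25%. These are shares of centres. Their share of patients would be smaller where low pre-approval counts reflect small size, but need not be for centres that started late.

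**Step 4: possible effect on the incidence.** Let p be the incidence in admitted centres, s the share of all post-approval patients who are in excluded centres, and r the risk in excluded centres relative to admitted ones. Then

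all-centre incidence = (1 - s)p + s·r·p = p[1 + s(r - 1)].

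The documents give neither s nor r. With s = 0.10 to 0.30 and r = 1.0 to 2.0 (assumptions):

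- r = 1.0: ratio 1.00 for any s
- s = 0.10, r = 1.5: 1 + 0.10 × 0.5 = 1.05
- s = 0.30, r = 2.0: 1 + 0.30 × 1.0 = 1.30
- r below 1: ratio below 1.00

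For scale, protocol 7 gives 2-7% for symptomatic haemorrhage in thrombolysed patients generally, not specifically in over-80s. The midpoint is 4.5%. The intervals are Wilson with continuity correction at n = 1000.

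| Reported | All-centre range | 95% CI of the reported figure |
|---|---|---|
| 2% | 2.0-2.6% | 1.3-3.1% |
| 4.5% | 4.5-5.9% | 3.3-6.0% |
| 7% | 7.0-9.1% | 5.5-8.8% |

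Under these assumptions the shift runs from nil to about the distance to the upper confidence limit, and slightly beyond it at 7%.

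**The case against.** The strongest defence is that the rule serves the comparison. Matching is not within centre and centre is not among the propensity variables, so requiring each centre to contribute to both periods is the main protection against a change in centre mix appearing as a period effect. This stands, and it is why the rule should stay for the pre/post analyses.

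Second, the both-period idea is not new in the SAP, because protocol 9.8 already asks for completeness in both groups. This also stands. The SAP's own addition is the count, which bites on centres with 1 to 4 patients.

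Third, the count refers to patients given IVT without repeating the age limit. If any age was meant, newly adopting centres would stay in. However, the pre- and post-approval groups are defined as over-80 groups, so the age-restricted reading is the natural one. The ambiguity is a reason to state the intention.

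Fourth, the rule may remove little. More frequent use does not mean use in new centres. Protocol 7 says the European guideline already recommended treatment in the elderly, and 5 patients in three years is low against a mean of about 17. The documents cannot settle this, and the SAP plans no count that would. The rule also works on registered patients, so an excluded centre may have treated over-80s earlier without entering five of them.

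**Conclusion.** The point holds as a restriction on coverage. On the natural reading, the post-approval incidence of SICH, death and independence describes only centres with at least 5 registered over-80 patients before approval, and no planned analysis shows what was left out. Any numerical effect is unknown: the factor of 1.00 to 1.30 rests wholly on the assumed s and r, and it falls below 1.00 if excluded centres have lower risk.

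A reader might infer three stronger things that the documents do not support.

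- That the incidence is biased towards reassurance. Nothing in either document says newly adopting centres have a higher SICH risk. They could select patients more cautiously.
- That the reported incidence is 5-23% too low. That range (1 - 1/1.05 to 1 - 1/1.30) appears only if a relative risk of 1 or below is ruled out in advance.
- That the pre/post relative risk is biased by the rule. With centre outside the propensity score, the rule protects that estimate.

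This is a cheap improvement to the descriptive part of the primary objective and does not count against the comparison.

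**What to change.** 1. Keep both both-period centre criteria (the count of 5 and the 70% follow-up) for the matched and unmatched pre/post comparisons.
2. For the single-cohort post-approval incidence with 95% CI, add an estimate that includes every centre meeting the 70% follow-up criterion in the post-approval period alone, with no pre-approval count or completeness requirement. Leave the patient-level, country-level and willingness criteria unchanged. State that this one table departs from the both-group completeness in protocol 9.8.
3. Report how many centres and patients the both-period criteria remove in each period.
4. State in SAP 4.1.2 that the 5 patients are over-80s.

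The data come from the existing registry. The cost is one extra table and somewhat noisier data from small or new centres. If few patients are removed, or the two incidence estimates agree, the sponsor can show that directly.

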4.1.3 At country level

- At least 500 patients registered from European mutual recognition procedure (MRP) countries
- Among MRP countries, one country could contribute a maximum of 30% of individual patient data to the MRP countries and a similar rules also applies for non-MRP countries, e.g. if the total number of patients from MRP countries is 500, then one MRP country could contribute a maximum of 150 patients and the similar rules also applies for non-MRP countries for each period separately. Date of stroke onset will be used to select the closest 30 % of patients around the approval date for pre – and post approval phase from each country. For the post-approval period, first 30% patients from start date and for the pre-approval period, latest 30% from approval date will be used,
- Countries date of approval varies. In most countries start date for prospective cohort is 1 July 2018 but in some countries approval dates are at a later time points. For MRP and Non-MRP countries the first day of the next months of the exact country approval date is used.

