What is the aim of the analyses: To show, if there are differences between pre- and post-approval populations in the safety, outcomes and in the baseline parameters?

Can differences in the outcomes be explained by differences in the baseline parameters?

Primary analyses: Propensity score matching should diminish differences in the outcomes if patients have balanced baseline parameters. If differences persist or an improvement or worsening of outcomes in the post approval phase occurs, other explanations are needed (as processes in the hospital (shorter or longer of door to needle time or increase of experience). This might need further exploration

Secondary analyses:

To confirm the results of the PS matching by adjusting the model parameter “post-approval vs pre-approval patient” for the most important imbalanced confounders for the outcomes of interest.

Descriptive statistics (absolute and relative frequencies for categorical variables, means, standard deviations, medians, inter quartile ranges, minimum and maximum for continuous/ordinal variables) for baseline, demographic characteristics and outcomes for all included patients will be provided separately for pre-approval and post-approval patients. In addition, 95% Wald confidence intervals will be provided for the continuous outcomes and Wilson score interval with continuity correction for binary outcomes. To compare difference among demographic and clinical baseline characteristics between pre-approval and post-approval, standardized differences will be used. Propensity score matching will be the primary statistical approach, multivariable modeling will be used for secondary complementary explorative analysis.

Primary Analysis

The primary analysis will be on propensity score matched patient datasets and we will compare the post-approval with the pre-approval patients regarding baseline demographics, clinical and radiological parameters, as well as treatment logistics, safety outcomes, functional outcome, and death.

Matched patient set constitute propensity score matched pair (1:1 greedy nearest neighbor matching using calipers equal to $0.2 \times \text{SD}$ of the logit of the propensity score)¹. The primary propensity score will be based on the variables listed below. These variables were selected based on established clinical significance and relevant SmPC criteria available in the SITS database.

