Age, sex, pre-stroke Modified Rankin Scale (mRS) score, baseline NIHSS score, systolic blood pressure and glucose level, antiplatelet treatment at stroke onset, history of hypertension, diabetes, atrial fibrillation, hyperlipidaemia, smoking and previous stroke earlier than 3 months, stroke onset to IVT treatment start time. We will include a baseline covariate only if 85% of the patients have a value reported.

A sensitivity PSM analysis will also be performed based on all baseline characteristics among patients with complete information. To determine whether the propensity score approach achieved balance in all potential confounders, we will compare all baseline characteristics of patients in the post-approval group to their propensity score matched pre-approval patients using standardized difference. If standardized difference >0.2 then propensity score model will be modified with inclusion of interactions and variable transformations to achieve better balance.

Relative risks for binary and mean difference for continuous/ordinal primary and secondary outcomes in post-approval vs pre-approval will be calculated together with 95% profile likelihood confidence intervals and likelihood ratio test p-values for relative risks and 95% Wald confidence intervals and Wald test p-values for mean differences.

Secondary Analysis

Secondary analysis will be on all patients fulfilling the inclusions-exclusions criteria.

Relative risks and mean difference for secondary outcomes in post-approval vs pre-approval will be calculated together with 95% confidence intervals and p-values.

Outcomes among post-approval vs pre-approval will be evaluated with generalized linear multivariable regressions with appropriate response distribution depending on outcome adjusting for potential confounders. Link function will be chosen as to estimate relative risks for binary outcomes and difference for continuous outcomes.

For each primary and secondary outcome covariates in models will be chosen according to the following:

- 1) Factors that contribute to the outcome of interest in an initial univariable analyses at p values <0.1 and variables known to influence outcomes such as age, sex, baseline NIHSS score and pre-stroke mRS, will be included in the multivariable model as candidate variables.
- 2) Final variables among the candidate variables with the outcome of interest will be selected by backward stepwise selection procedures using a p value <0.05 .

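### Country and MRP status are missing from the primary propensity score and the matching rule, although the selection rules let country mix differ between the two periods

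*SAP*

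**What the plan says.** SAP 4.1.3 limits any one country to 30% of its group (MRP or non-MRP). The example reads: "one MRP country could contribute a maximum of 150 patients and the similar rules also applies for non-MRP countries for each period separately". SAP 4 asks for at least 500 MRP patients in each period out of roughly 1000, without fixing the MRP share. Start dates are staggered: "In most countries start date for prospective cohort is 1 July 2018 but in some countries approval dates are at a later time points". SAP 3.1 ends the post-approval period in June 2021 for everyone.

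Under Planned Analysis, Primary Analysis, the score rests on a closed list of 14 variables, beginning "Age, sex, pre-stroke Modified Rankin Scale (mRS) score, baseline NIHSS score, systolic blood pressure and glucose level, antiplatelet treatment at stroke onset" and ending with onset-to-treatment time. The stated basis is: "These variables were selected based on established clinical significance and relevant SmPC criteria available in the SITS database". Matching is 1:1 on the logit of that score. Country, centre and MRP status appear in neither place, although Appendix 1 lists country name among the study's important variables.

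Three other provisions are open-ended:
- Balance check: "we will compare all baseline characteristics of patients in the post-approval group to their propensity score matched pre-approval patients using standardized difference".
- Sensitivity matching: "A sensitivity PSM analysis will also be performed based on all baseline characteristics among patients with complete information".
- Secondary models: factors passing a univariable screen plus "variables known to influence outcomes such as age, sex, baseline NIHSS score and pre-stroke mRS", followed by backward selection.

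On imbalance the SAP says: "If standardized difference >0.2 then propensity score model will be modified", by means of interactions and transformations. Protocol 9.7.1 puts every baseline characteristic into the score but does not name country. Both documents allow an optional sensitivity analysis by European and non-European origin.

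**The concern.** The primary result is the matched pre/post contrast. Three rules let country mix drift between the arms of that contrast: a ceiling applied to each period on its own, an MRP floor without a fixed share, and a shorter post-approval window for countries approved late. If countries differ in outcome for reasons beyond the 14 listed covariates, a change in which countries contribute will look like a change after approval.

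The SAP says that differences persisting after matching need other explanations, and it suggests hospital processes or growing experience. Country mix is a competing explanation that can be checked with data already extracted. The text does not ensure that it will be. If the balance check did flag country, interactions and transformations of the listed variables would not clearly bring in a variable that is outside the model. The European/non-European analysis is optional and cannot address mix within Europe.

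**Working it through.** **Plan's own figure.** 0.30 × 500 = 150, as printed in SAP 4.1.3. There is no power calculation to reproduce.

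**Inputs.** From the documents: a 36-month post-approval window (July 2018 to June 2021), a pre-approval window of about 3 years, the 0.2 balance limit, and SICH in 2-7% of treated patients (Protocol 7). Assumed: a late country supplies a fraction f = 0.20-0.25 of its group's monthly flow; approval delay d is 6, 12 or 24 months; 900 matched pairs.

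**Share shift.** Pre-approval share = f. Post-approval share = f(36−d) / [f(36−d) + 36(1−f)]. For f = 0.25 and d = 12: 6 / (6 + 27) = 0.182, a fall of 6.8 points.

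**Standardized difference** = |p−q| / √{[p(1−p) + q(1−q)]/2}. With p = 0.25 and q = 0.182: 0.068 / 0.410 = 0.166. If the country's group is half of the set, both shares are halved.

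| Delay | Shift in share of group (points) | Std. difference, group is whole set | Group is half of set |
|---|---|---|---|
| 6 months | 2.8-3.3 | 0.07-0.08 | about 0.05 |
| 12 months | 5.7-6.8 | 0.15-0.17 | 0.10-0.11 |
| 24 months | 12.3-15.0 | 0.36-0.40 | 0.24-0.27 |

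Solving for the delay that reaches 0.2 gives about 14-15 months if the group is the whole set, and about 20-21 months if it is half.

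**MRP share.** The same formula gives 0.20 for 50% against 60%, 0.21 for 60% against 70%, and 0.23 for 70% against 80%.

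**Bias with no true change.** Rate in each period = base + share × gap; RR = post/pre; the false-positive rate comes from a two-sided 5% Wald test on log RR with 900 per group. The late country is assumed to do worse. Independence, 35% elsewhere, 15-point gap, f = 0.25, d = 12:
- Pre: 0.35 − 0.25 × 0.15 = 0.3125. Post: 0.35 − 0.182 × 0.15 = 0.3227. RR = 1.033.
- SE of log RR = 0.069, so the 95% interval runs from about 13% below to 14% above the estimate. False positives 7.5%.
- Group is half of the set: RR = 0.3364 / 0.3313 = 1.015, false positives 5.6%.
- With a 3-point gap and f = 0.20: RR 1.005, false positives 5.1%.

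Other outcomes at 12 months, worst case tried: mortality (20% elsewhere, 15-point gap) RR 0.957, or 0.977 if half, with false positives 8.1% or 5.8%; SICH (2% elsewhere, 2-point gap) RR 0.945, or 0.970 if half, with false positives 5.4% or 5.1%.

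At 24 months with the 15-point gap: independence RR 1.07, or 1.03 if half (false positives 17% or 8%); mortality RR 0.91, or 0.95 if half (21% or 9%).

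**The case against.** The strongest reply is that drift is already limited and the effect is minor. Most countries start on 1 July 2018. Each centre must have at least 5 patients in both periods. A country at its cap in both periods keeps its share of its group. Patients from large countries are taken close to their own approval date. The analyses are called descriptive and exploratory, and the optional regional analysis bears on a change in MRP share. All of this stands and keeps the point modest, but none of these rules equalises country shares.

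A second reply is that country could fall under the wording on all baseline characteristics, since Appendix 1 lists it. That is a fair reading of the balance check and the sensitivity matching. It does not reach the primary score, whose list is closed.

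A third reply concerns the remedy. At 2-7% of about 2000 patients there would be roughly 40-140 SICH events. Spread over the 19 countries named in the protocol, the low end is about two per country, so unpooled country terms in a relative-risk model could be unstable. This is right, and the fix allows for it.

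A reader might also infer that late-approving countries have a pre-approval window stretching from June 2015 to their own approval date, which would enlarge the imbalance. That joins a start date from SAP 3.1 to an end date from 4.1.1 and conflicts with the period of about 3 years given in both sections. No figures here rest on it.

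**Conclusion.** The omission from the primary score and the matching is plain on the page, and the rules permit country mix to differ. Elsewhere the role of country is unclear, not excluded.

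The documents do not show that the mix will differ, nor that the primary comparison is seriously confounded; a reader might infer either. With a 12-month delay, a single large country stays below the SAP's 0.2 limit, and the resulting bias is well inside the width of the confidence interval. Of the delays tried, only 24 months exceeds 0.2. No passage supports a delay of that length, or one at the 14-21 month crossing points. The larger biases also need a 15-point residual gap between countries, which nothing in the documents supports. A 10-point change in MRP share reaches the 0.2 limit without any delay, but the documents give no shares either.

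This is a worthwhile, inexpensive safeguard and not a fatal flaw. The sizes depend on the assumed flows, delays, base rates and gaps; confidence is moderate.

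**What to change.** 1. Add country to the primary propensity score. Pool small countries within MRP or within non-MRP, by a rule stated in the SAP. The existing rebalancing step then applies to country as well.
2. Name country and MRP status in the standardized-difference check, with the existing 0.2 limit, and tabulate both by period before and after matching. This part costs no pairs.
3. In the unmatched models for mortality and the mRS outcomes, keep the same pooled country factor outside the p<0.1 screen and the backward selection. For SICH, use MRP status or a coarser grouping, because events are few.

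The change is SAP wording only, since country is already extracted. The price is somewhat fewer pairs and slightly wider intervals where the mix has shifted. A matching simulation (60 runs, 1000 patients per period, 8 countries, 3-year pre-window, 14 covariates with small shifts) compared scores with and without country:
- One country 12 months late: 871 to 850 pairs (2% fewer, SE about 1% larger); largest country standardized difference 0.16 to 0.03.
- One country 24 months late: 875 to 804 pairs (8% fewer, SE 4% larger); 0.39 to 0.03.
- Two countries 24 months late: 872 to 743 pairs (15% fewer, SE 8% larger); 0.37 to 0.04.

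These losses may not carry over to a larger number of countries, which is a further reason to fix the pooling rule in advance.
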